**14.3.4. Supportive Care Guidelines for Events of Clinical Interest/Immune Related Adverse Events (IRAEs)**

Patient should receive appropriate supportive care measures as deemed necessary by the treating investigator, including but not limited to the items outlined below:

**Diarrhea:** Patients should be carefully monitored. Patients can receive aggressive anti-diarrheal agents, including and not limited to: loperamide and atropine/diphenoxylate.

- All subjects who experience diarrhea/colitis should be advised to drink liberal quantities of clear fluids. If sufficient oral fluid intake is not feasible, fluid and electrolytes should be substituted via IV infusion.

**Nausea/vomiting:** Nausea and vomiting should be treated aggressively, and consideration should be given in subsequent cycles to the administration of prophylactic antiemetic therapy according to standard institutional practice. Patients should be strongly encouraged to maintain liberal oral fluid intake.

**Anti-infectives:** Patients with a documented infectious complication should receive oral or IV antibiotics or other anti-infective agents as considered appropriate by the treating investigator for a given infectious condition, according to standard institutional practice.

**Bone Marrow Support:** Pegfilgrastim can be administered on day 6, 7 or 8 of every cycle at the discretion of the investigator. Pegfilgrastim can be initiated at cycle 1 or after neutropenia is observed. There are no contraindications to blood transfusions.

#### 14.4. OTHER CONSIDERATIONS

##### 14.4.1. Contraception

Pembrolizumab may have adverse effects on a fetus in utero. Furthermore, it is not known if pembrolizumab (MK-3475) has transient adverse effects on the composition of sperm.

For this study, male subjects will be considered to be of non-reproductive potential if they have azoospermia (whether due to having had a vasectomy or due to an underlying medical condition).

Female subjects will be considered of non-reproductive potential if they are either:

- (1) Postmenopausal (defined as at least 12 months with no menses without an alternative medical cause; in women <45 years of age a high follicle stimulating hormone (FSH) level in postmenopausal range may be used to confirm a post-menopausal state in women not using hormonal contraception or hormonal replacement therapy. In the absence of 12 months of amenorrhea, a single FSH measurement is insufficient.);

OR

- (2) Have had a hysterectomy and/or bilateral oophorectomy, bilateral salpingectomy or bilateral tubal ligation/occlusion, at least 6 weeks prior to screening;

OR

- (3) Has a congenital or acquired condition that prevents childbearing.

Female and male subjects of reproductive potential must agree to avoid becoming pregnant or impregnating a partner, respectively, while receiving study drug and for 120 days after the last dose of study drug by complying with one of the following:

- (1) Practice abstinence\* from heterosexual activity;

OR

- (2) Use (have their partner use) acceptable contraception during heterosexual activity.

The following are considered acceptable barrier methods of contraception:

Single method (one of the following is acceptable):

- Intrauterine device (IUD)
- Vasectomy of a female subject's male partner
- Contraceptive rod implanted into the skin

Combination method (requires use of two of the following):

- Diaphragm with spermicide (cannot be used in conjunction with cervical cap/spermicide)
- Cervical cap with spermicide (nulliparous women only)
- Contraceptive sponge (multiparous women only)
- Male condom or female condom (cannot be used together)
- Hormonal contraceptive: oral contraceptive pill (estrogen/progestin – only pill), contraceptive skin patch, vaginal contraceptive ring, or subcutaneous contraceptive injection)

\*Abstinence (relative heterosexual activity) can be used as the sole method of contraception if it is consistently employed as the subject's preferred and usual lifestyle and if considered acceptable by local regulatory agencies and ERCs/IRBs. Periodic abstinence (e.g. calendar, ovulation, sympto-thermal, post-ovulation methods, etc.) and withdrawal are not acceptable methods of contraception.

\*If a contraceptive method listed above is restricted by local regulations/guidelines then it does not qualify as an acceptable method of contraception for subjects participating at sites in this country/region.

Patients should be informed that taking the study medication may involve unknown risks to the fetus (unborn baby) if pregnancy were to occur during the study. In order to participate in the study patients of childbearing potential must adhere to the contraception requirement (described above) from the day of study medication initiation (or 14 days prior to the initiation of study medication for oral contraception) throughout the study period up to 120 days after the last dose of study therapy. If there is any question that a patient of childbearing potential will not reliably comply with the requirements for contraception, that patient should not be entered into the study.

#### **14.4.2. Use in Pregnancy**

If a patient inadvertently becomes pregnant while on treatment with pembrolizumab (MK-3475), the subject will immediately be removed from the study. The site will contact the patient at least monthly and document the subject's status until the pregnancy has been completed or terminated. The outcome of the pregnancy will be reported to AFT without delay and within 24 if the outcome is a serious adverse experience (e.g., death, abortion, congenital anomaly, or other disabling or life-threatening complication to the mother or newborn).

The study investigator will make every effort to obtain permission to follow the outcome of the pregnancy and report the condition of the fetus or newborn to AFT. If a male patient impregnates his female partner the study personnel at the site must be informed immediately and the pregnancy reported to AFT and followed as described above. AFT will report pregnancy outcomes to Merck.

#### 14.4.3. Use in Nursing Women

It is unknown whether pembrolizumab is excreted in human milk. Since many drugs are excreted in human milk, and because of the potential for serious adverse reactions in the nursing infant, patients who are breast-feeding are not eligible for enrollment.

### 15. MEASUREMENT OF EFFECT

This randomized phase II study will evaluate PFS as the primary endpoint based on RECIST 1.1, which will be used for assessment of tumor response.

#### 15.1. SCHEDULE OF EVALUATIONS

The initial tumor imaging will be performed within 14 days prior to the first dose of study treatment. Scans performed as part of routine clinical management are acceptable for use as the screening scan if they are of diagnostic quality and performed within 14 days prior to the first dose of study treatment. On-study imaging will be performed every 6 weeks ( $42 \pm 7$  days) after the first dose of study treatment or more frequently if clinically indicated. The timing for imaging studies should **follow calendar days** and should not be adjusted for delays in cycle starts or extension of topotecan or pembrolizumab (MK-3475) cycle frequencies. The same imaging technique should be used in a patient throughout the study.

After the first documentation of progression while receiving pembrolizumab (MK-3475) alone it is at the discretion of the investigator to keep a clinically stable patient on study treatment or to stop study treatment until repeat imaging performed 4-6 weeks later confirms progression.

Clinical stability in a patient whose disease displays radiographic progression is defined as:

- Absence of symptoms and signs indicating clinically significant progression of disease (including worsening laboratory values).
- NO decline in ECOG performance status.
- Absence of rapid progression of disease or progressive tumor at critical anatomical sites (e.g. cord compression) requiring urgent alternative medical intervention.

Patients that are deemed clinically unstable are not required to have repeat imaging for confirmation. Upon repeat imaging, if progression is confirmed, then the patient will be discontinued from study treatment. As the primary endpoint is PFS, the date of the first scan that documented progression should be used. If progression is not confirmed, then the patient should resume/continue study treatment and have the next scan according to the every 6-week ( $42 \pm 7$  days) schedule from the first dose of study treatment. When feasible, patients should not be discontinued until progression is confirmed.

For patients who discontinue study treatment for reasons other than disease progression, imaging should continue according to the same schedule (every 6 weeks/ 42 ± 7 days) until the patient experiences confirmed disease progression or starts a new antineoplastic therapy.

Study eligibility will be according to RECIST 1.1 criteria.

**15.1.1. Response for Evaluation Criteria in Solid Tumors (RECIST) 1.1  
Criteria for Evaluating Response in Solid Tumors**

RECIST Version 1.1\* will be used in this study for assessment for tumor response.

\*As published in the European Journal of Cancer

**15.1.2. Response for Evaluation Criteria in Solid Tumors (RECIST) 1.1  
Criteria for Evaluating Response in Solid Tumors**

**Measurable Disease**

A non-nodal lesion is considered measurable if its longest diameter can be accurately measured as  $\geq 2.0$  cm with chest x-ray, or as  $\geq 1.0$  cm with CT scan,

A superficial non-nodal lesion is measurable if its longest diameter is  $\geq 1.0$  cm in diameter as assessed using calipers (e.g. skin nodules) or imaging. In the case of skin lesions, documentation by color photography, including a ruler to estimate the size of the lesion, is recommended.

A malignant lymph node is considered measurable if its short axis is  $\geq 1.5$  cm when assessed by CT scan (CT scan slice thickness recommended to be no greater than 5 mm).

Lesions that are previously irradiated must show clear evidence of progression to be considered as measurable disease.

**Non-Measurable Disease**

All other lesions (or sites of disease) are considered non-measurable disease, including pathological nodes (those with a short axis  $\geq 1.0$  to  $< 1.5$  cm). Bone lesions, leptomeningeal disease, ascites, pleural/pericardial effusions, lymphangitis cutis/pulmonis, inflammatory breast disease, and abdominal masses (not followed by CT), are considered as non-measurable as well.

Note: 'Cystic lesions' thought to represent cystic metastases can be considered as measurable lesions, if they meet the definition of measurability described above. However, if non-cystic lesions are present in the same patient, these are preferred for selection as target lesions. In addition, lymph nodes that have a short axis  $< 1.0$  cm are considered non-pathological (i.e., normal) and should not be recorded or followed.

**15.1.3. Guidelines for Evaluation of Measurable Disease**

**Measurement Methods:**

- All measurements should be recorded in metric notation (i.e., decimal fractions of centimeters) using a ruler or calipers.
- The same method of assessment and the same technique must be used to characterize each identified and reported lesion at baseline and during follow-up. For

patients having only lesions measuring at least 1 cm to less than 2 cm must use CT imaging for both pre- and post-treatment tumor assessments.

- Imaging-based evaluation is preferred to evaluation by clinical examination when both methods have been used at the same evaluation to assess the antitumor effect of a treatment.

#### **Acceptable Modalities for Measurable Disease:**

Conventional CT: This guideline has defined measurability of lesions on CT scan based on the assumption that CT slice thickness be at least 2.5 mm but no greater than 5 mm.

#### **Measurement at Follow-up Evaluation:**

- A subsequent scan must be obtained not less than 4 weeks following initial documentation of an objective status of either complete response (CR) or partial response (PR).
- In the case of stable disease (SD), follow-up measurements must have met the SD criteria at least once after study entry at a minimum interval of not less than 6 weeks.
- The cytological confirmation of the neoplastic origin of any effusion that appears or worsens during treatment when the measurable tumor has met criteria for response or stable disease is mandatory to differentiate between response or stable disease (an effusion may be a side effect of the treatment) and progressive disease.
- Cytologic and histologic techniques can be used to differentiate between PR and CR in rare cases (e.g. residual lesions in tumor types such as germ cell tumors, where known residual benign tumors can remain.)

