Study Design	This is a multi-institutional, randomized, open-label phase II study of pembrolizumab compared to topotecan, administered to patients with SCLC who have progressed or relapsed after first-line treatment with etoposide and platinum. Patients will be randomized in a 2:1 fashion to receive pembrolizumab or topotecan. Participants in the topotecan arm that progress will be allowed to cross-over to the pembrolizumab arm.
Study Treatment Plan	Pembrolizumab Arm: Pembrolizumab will be administered via IV infusion at 200 mg every 3 weeks, and treatment continued for up to 24 months, until documented disease progression, unacceptable side effects or intercurrent illness that prevents further administration of treatment, investigators' decision to

	
withdraw the subject, subject withdraws consent, pregnancy of the patient, noncompliance of the patient, or for administrative reasons.
 
Topotecan Arm: Topotecan will be administered via IV infusion at 1.25 mg/m^2 on days 1 to 5 of a 3-week cycle. Pegfilgrastim may be given on day 6, 7, or 8 to offset neutropenia. Patients who progress in the topotecan arm will be allowed to cross-over to the pembrolizumab arm.

Efficacy Assessments	
Patients will be evaluated every 6 weeks (42 ± 7 days) with radiographic imaging to assess response to treatment. Investigators will make all treatment-based decisions using RECIST 1.1.

Safety Assessments	
Patients will be evaluated clinically by physical exam and with routine blood work every 21 days. Adverse events will be monitored throughout the Study and graded in severity according to the guidelines outlined in the NCI Common Terminology Criteria for Adverse Events (CTCAE) version 4.

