## **9.2. TUMOR IMAGING SCHEDULE**

The initial tumor imaging will be performed within 14 days prior to the first dose of study treatment. Scans performed as part of routine clinical management are acceptable for use as the screening scan if they are of diagnostic quality and performed within 14 days prior to the first dose of study treatment.

On-study imaging will be performed every 6 weeks ( $42 \pm 7$  days) after the first dose of study treatment, or more frequently if clinically indicated. The timing for imaging studies should follow calendar days and should not be adjusted for delays in cycle starts or extension of pembrolizumab (MK-3475) or topotecan cycle frequencies. The same imaging technique should be used in a patient throughout the study. Local reading (investigator assessment with site radiology reading) will be used to determine eligibility and for patient management.

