**Table 4. Study Treatment**

Drug	Dose/ Potency	Dose Frequency	Route of Administration	Regimen/ Treatment Period	Use
Pembrolizumab	200 mg	Every 3 weeks	IV Infusion	Day 1 of each 3 week cycle	Experimental
Topotecan	1.25 mg/m  Days 1 to 5	Every 3 weeks	IV Infusion	Days 1-5 of each 3 week cycle	Standard/ Control

The pembrolizumab (MK-3475) dosing interval may be increased due to toxicity.

Study treatment should begin on the day of randomization and no later than 48 hours from the date on which treatment is allocated/assigned (or 72 hours if randomization occurs on a Friday).

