### Evaluation of Target Lesions

- **Complete Response (CR):** All of the following must be true:
  - a. Disappearance of all target lesions.
  - b. Each target lymph node must have reduction in short axis to < 1.0 cm.
- **Partial Response (PR):** At least a 30% decrease in PBSD (sum of the longest diameter for all target lesions plus the sum of the short axis of all the target lymph nodes at current evaluation) taking as reference the BSD.
- **Progression (PD):** At least one of the following must be true:
  - a. At least one new malignant lesion, which also includes any lymph node that was normal at baseline (< 1.0 cm short axis) and increased to  $\geq$  1.0 cm short axis during follow-up.
  - b. At least a 20% increase in PBSD (sum of the longest diameter for all target lesions plus the sum of the short axis of all the target lymph nodes at current evaluation) taking as reference the MSD. In addition, the PBSD must also demonstrate an absolute increase of at least 0.5 cm from the MSD.

- **Stable Disease (SD):** Neither sufficient shrinkage to qualify for PR, nor sufficient increase to qualify for PD taking as reference the MSD.

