## 20. STATISTICAL ANALYSIS PLAN

The primary analysis will include all randomized patients but exclude ineligible patients or patients who cancel this study before receiving any protocol treatment.

The primary efficacy endpoint is PFS, which is defined as the time from the date of randomization to the date of earliest radiographic disease progression or death. If the subject does not experience radiographic disease progression or death, then the data will be censored at the date of the last disease assessment. PFS will be analyzed by Kaplan Meier methodology and compared between arm E and arm C, using a log-rank test stratified by disease type (sensitive vs refractory). A two-sided, stratified log-rank test P value will be provided. Median PFS time will be calculated and 95% confidence interval for median PFS will be presented. Overall survival (OS) will be analyzed in a similar manner as PFS.

Late treatment effect is often expected for immunotherapy. For this reason, a weighted log rank test with Harrington-Fleming weights that optimize the expected late treatment effect will be conducted as a supplementary analysis for both PFS and OS. In particular, the following three parameter settings will be used: (1)  $\rho = 0$  and  $\gamma = 0.5$ ; (2)  $\rho = 0$  and  $\gamma = 1$ ; and (3)  $\rho = 0$  and  $\gamma = 2$  (39).

The proportion of subjects with objective response as assessed by the investigator using RECIST version 1.1 will be evaluated for randomized subjects. The objective response rate will be estimated and compared between arm E and arm C, using a Cochran-Mantel-Haenszel (CMH) test stratified by tumor volume. A two-sided, stratified CMH test P value will be provided. In addition, a 95% confidence interval will be constructed for the estimated proportions. Similar analysis will be conducted for disease control rate (DCR), which is defined as the proportion of patients achieving complete, partial and stable disease after the protocol treatment.

All subjects who receive at least one dose of the study drug will be included in safety analysis. Treatment-related toxicity will be summarized by grade, type and system organ

class. Comparisons of the percentages of subjects experiencing an adverse event between arm E and arm C will be performed using Fisher's exact test.

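### The 6-week minimum for stable disease has no tolerance and does not fit the 42 ± 7 day scan window, so disease control status can depend on the appointment date

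*Combined protocol and SAP*

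**What the plan says.** **SD rule.** Section 15.1.3, under Measurement at Follow-up Evaluation, says of SD that "follow-up measurements must have met the SD criteria at least once after study entry at a minimum interval of not less than 6 weeks". It allows no tolerance, and study entry is not defined.

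**Scan schedule.** The synopsis (Section 1.1) says: "Patients will be evaluated every 6 weeks (42 ± 7 days) with radiographic imaging to assess response to treatment". Section 9.2 sets the anchor: "On-study imaging will be performed every 6 weeks", with the 42 ± 7 day window, "after the first dose of study treatment, or more frequently if clinically indicated". Section 15.1 repeats this.

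**Gap between randomization and first dose.** Under Table 4: "Study treatment should begin on the day of randomization and no later than 48 hours from the date on which treatment is allocated/assigned", extended to 72 hours after a Friday randomization.

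**Endpoint.** Section 20 defines "disease control rate (DCR), which is defined as the proportion of patients achieving complete, partial and stable disease after the protocol treatment". DCR is analysed in the same way as ORR: in randomized subjects, with a stratified CMH test between arms, a two-sided P value and 95% confidence intervals. No minimum SD duration is given there. The SD criterion for target lesions in Section 15.1.4, "Neither sufficient shrinkage to qualify for PR, nor sufficient increase to qualify for PD taking as reference the MSD", and Table 11 also carry no time minimum.

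**The concern.** The SD minimum equals the nominal scan time, while the scan itself may be up to a week early. Of two patients with the same tumour course, both stable at the first scan and progressed at the second, the one imaged on day 38 has no qualifying SD and the one imaged on day 43 does. Both were scanned on schedule.

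DCR is compared formally between arms. The exposed patients are those who have an event between the first and second scan, and the planning assumptions put more of them in the topotecan arm, so the loss need not cancel. Section 20 also does not say how to classify a patient whose only SD scan is early. Two analysts could report different DCRs from the same data, and in an open-label trial that choice should be fixed in advance.

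**Working it through.** **1. The window.** 42 − 7 = 35 and 42 + 7 = 49, so the first scan falls on days 35 to 49 (15 days). The second falls at 84 ± 7, that is days 77 to 91. Six weeks is 6 × 7 = 42 days.

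**2. How many compliant days are too early.** This depends on what study entry means:

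| Study entry taken as | First-scan days under 42 days from entry |
|---|---|
| First dose | 7 of 15 (days 35–41) |
| Randomization, 1 day before first dose | 6 of 15 |
| Randomization, 2 days before | 5 of 15 |
| Randomization, 3 days before | 4 of 15 |
| Registration or consent, 7 or more days before | 0 of 15 |

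**3. Inputs for size.** The plan gives no expected value, sample size or power for DCR, so its PFS assumptions are used (Section 19.1): exponential PFS, medians of 20 weeks (arm E, pembrolizumab) and 12 weeks (arm C, topotecan), with 62 and 31 patients. As a check on these inputs, the hazard ratio is 12/20 = 0.60. With 86 events, 2:1 allocation and one-sided 0.10, √(86 × 2/3 × 1/3) × |ln 0.60| − 1.282 = 2.233 − 1.282 = 0.951, which gives 82.9% power against the stated 82%.

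**4. Share exposed if the first scan is early.** Take the first scan on day 38 (middle of days 35–41) and the second on day 84. With S(t) = 2^(−t/median) and day 38 = 5.43 weeks:

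- E: S(5.43) − S(12) = 0.828 − 0.660 = 0.169 (10.5 of 62)
- C: S(5.43) − S(12) = 0.731 − 0.500 = 0.231 (7.2 of 31)

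The 66% (E) and 50% (C) still event-free at the second scan cannot be affected.

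**5. Loss of DCR.** Multiply by the share of first scans that are early. The documents do not give this share, so a range is shown, taken as equal in both arms:

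| Share early (assumed) | E, points (patients) | C, points (patients) | C minus E, points |
|---|---|---|---|
| 10% | 1.7 (1.0) | 2.3 (0.7) | 0.6 |
| 25% | 4.2 (2.6) | 5.8 (1.8) | 1.6 |
| 47% (7/15, scan days uniform) | 7.9 (4.9) | 10.8 (3.3) | 2.9 |

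If every first scan were early, the losses would be 16.9 and 23.1 points.

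**6. Limits of the model.** Everyone event-free at the first scan is treated as SD. Early responders are ignored, which overstates the loss. Patients who are event-free but have no further evaluable scan are not included, which understates it.

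**7. After the change.** With a minimum of 35 days from first dose, 0 of the 15 window days are too early.

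**The case against.** **The 6-week rule may not govern DCR.** Section 20 does not cite it, and Section 15.1.4 refers the reader to the statistical section for formal definitions of analysis variables. A reader might infer that the plan counts early SD as failure in DCR. The documents do not say so. It follows only if the Section 15.1.3 rule is carried into Section 20, which is the natural reading but an unstated one. This stands as a limit on the claim. It does not remove the need to settle the question.

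**Few patients are exposed.** A reader might also infer that compliant patients with SD are lost in general. They are not: SD has to be met only once, so SD at the second or a later scan qualifies, and a later response counts in its own right. This stands.

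**The anchor is undefined.** Step 2 shows that the mismatch disappears if study entry is at least a week before first dose, and Table 2 allows consent up to 21 days before treatment. This also stands, and is a reason to name the anchor.

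**The effect is small.** Scans are aimed at day 42, so the 47% share has no support in the documents. A between-arm shift of at most about 3 points is small beside a standard error of about 11 points: √(0.25/62 + 0.25/31) = 0.110, assuming DCR near 50%. DCR is not among the Section 6 objectives. This is fair, and keeps the point minor.

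**A strict minimum is defensible.** A patient with SD on day 37 and progression at the next scan has not been shown to be stable for 6 weeks. That is true, but the strict rule then treats equally compliant patients differently according to the scan date.

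**Conclusion.** The point holds, with low consequence. The SD minimum and the scan window do not fit together if study entry means first dose or randomization. If the minimum is applied to DCR, a patient with a single early SD scan and no later SD or response is classified by appointment date rather than tumour behaviour.

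Under the planning medians and the simplifications above, the loss runs from about 1.7 (pembrolizumab) and 2.3 (topotecan) points to about 7.9 and 10.8 points, for assumed early shares of 10% and 47%. The between-arm difference in DCR moves in favour of pembrolizumab by about 0.6 to 3 points. The higher figures should not be read as strict upper bounds, because they depend on the assumed share and scan days. PFS and ORR are untouched.

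**What to change.** In Section 15.1.3, replace the minimum of 6 weeks after study entry with 35 days from first dose. That is the scheduled 6-week scan less its 7-day window, counted from the same anchor as the scans, and it removes the undefined term. In Section 20, add one sentence saying that this minimum defines SD for DCR, which also settles how a patient with only one SD scan is classified.

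The cost is two short text changes, with no new data, visits or patients. The downside is that SD is accepted up to a week earlier than now.
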